7.7.2 Laboratory data

The analyses of laboratory data will be descriptive in nature and will be based on BI standards (see [\[5\]](#)) The CTCAE grade will be calculated for each lab value (see section [9.2](#)).

The baseline, last value on treatment and corresponding change from baseline will be presented using N, median and interquartile range. This will be done for all continuous laboratory parameters using the BI normalised values, except, however, in the case of WBC differentials (Neutrophils and Lymphocytes) which have been recorded in percentage. These have been re-derived to normalised values in such a way that the accuracy of decimal places is maintained for longer. This is documented in section [9.2](#).

Patients with clinically relevant laboratory abnormalities, as defined in section [9.1](#) will be summarised. Project-specific rules for flagging possible clinically significant abnormal laboratory values will be applied.

Patients will be counted under the initial treatment group. Separate listings for patients treated under different doses will be created. Thereby the data will be reported under course regimen. The analysis of lab data will use the same analyzing treatment periods as described for the AEs.

Single time courses by treatment regimen will be used to display laboratory values over time. The graphs may be truncated if no sufficient data is available. These graphs will be produced for absolute neutrophile count, platelets, Creatinine phosphokinase, haemoglobin, and for other laboratory parameters (*if considered important in this trial, decision will be given in URPM of the final analysis*).

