1.4 BENEFIT - RISK ASSESSMENT

Patients with AML that are considered ineligible for intensive treatment at initial diagnosis as well as patients with relapsed/refractory AML have an overall adverse prognosis with very limited treatment options. LD-Ara-C is an established treatment for these patients, but outcome results are not satisfactory; in previously untreated patients considered ineligible for intensive treatment complete remissions up to 18% ([R07-2771](#)) were reported with LD-Ara-C treatment.

As no objective criteria are established to assess a patient's eligibility for intensive treatment the decision which treatment to adopt is based on the specialised investigators medical experience. To allow continuous monitoring and periodic reporting of the reasons why patients are assessed ineligible for intensive treatment the rationale for decision-making will be documented by the investigator for every single patient entered in the trial.

The most relevant side effect of BI 6727 administration is expected to be a transient inhibition of proliferation of normal dividing cells in bone marrow and mucosal tissue. Thymic atrophy seen in toxicological studies is not deemed relevant in the target population of adult cancer patients. Inhibition of mucosal proliferation may lead to gastrointestinal symptoms such as nausea or diarrhoea. The side effects on bone marrow stem cells may lead

to a temporary decrease of blood cells and platelets. These side effects are frequently seen in cancer patients treated with conventional cytotoxics or targeted therapies and can easily be monitored. Supportive treatment for these effects is available. In contrast to many established antiproliferative agents no unspecific toxic effects have been identified for BI 6727 in preclinical studies. AML patients often present with disease-related cytopenias, which without effective therapy will aggravate as the disease progresses. For most anti-leukaemia therapeutics, a drug-related transient worsening of cytopenias is common and inevitable. As described above, transient cytopenias are expected to occur with BI 6727. Cytarabine treatment is known to cause toxicities that overlap with BI 6727. Therefore, the CTCAE (common terminology criteria for adverse events) grade and duration of cytopenias and gastrointestinal toxicity will be important safety criteria to limit the risk of the treatment with the trial drugs (see section 5.2).

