4.1.4 Selection and timing of doses for each patient

Prior to inclusion of a new patient in the phase I part the investigator has to confirm the actual dose tier of BI 6727 for the patient with the clinical monitor of the sponsor who oversees the dose escalation steps according to the safety data of patients from all trial sites.

BI 6727 will be administered as an intravenous infusion under the supervision of the investigator or designated personnel. Subcutaneous cytarabine injections will be administered according to the SPC.

The trial drugs may be administered at any time during the day. In case the second dose of BI 6727 is missed for administrative reasons the respective dose will be administered on the following two days. In case a dose of cytarabine is missed for administrative reasons the respective dose will not be administered at a later time (any missed cytarabine dose must be documented in the eCRF).

At the end of each treatment cycle, the response to treatment will be assessed. To continue treatment with further cycles, the following criteria must be met:

- 1.) Absence of disease progression (see [section 5.1.1](#))
- 2.) Neutrophils $\geq 500 / \mu\text{L}$ ($0.5 \times 10^9 / \text{L}$) and platelets $\geq 25,000 / \mu\text{L}$ ($25 \times 10^9 / \text{L}$); unless CTCAE grade 4 neutropenia or thrombopenia was preexistent
- 3.) Acceptable tolerability (in case of DLT, patients may continue therapy only after recovery from DLT to CTCAE levels which allow further therapy and only with a reduced dose), and recovery from drug-related cardiac toxicity.

In case criterion 2 is not fulfilled, the peripheral blood should be re-evaluated for up to three weeks. As soon as criterion 2 is met the treatment should be continued (unless other criteria for discontinuation or withdrawal apply, see [section 6.3](#)). A delay of haematopoietic reconstitution (i.e criterion 2 unmet) for more than three weeks after the end of the treatment cycle qualifies for DLT in patients with CRi or PR (see [section 5.2.3](#)). Any case of a delay in treatment cycle should be communicated to the clinical monitor of Boehringer Ingelheim. Progressive disease will lead to discontinuation of treatment.

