7.3.3 Safety analyses

The occurrence of dose limiting toxicity (DLT) as well as the incidence and intensity of adverse events graded according to CTCAE, laboratory parameters, vital signs and duration of neutropenia will be evaluated.

All patients of the full analysis set (both phase I and phase II) will be included in the safety analyses.

Two analyses will be performed. The first analysis of safety will be performed for the first part of the trial (determination of the MTD, first cycle only, treatment regime=initial dose at the start of the treatment, full analysis set (phase I only)). This descriptive analysis will evaluate the MTD for each treatment schedule. The second analysis will be performed with

respect to all cycles and will act as a support for the determination of the MTD (full analysis set (both phase I and phase II)).

Incidence and intensity of adverse events

The severity, and timing of adverse events will indicate how well the treatment regimen is tolerated. Toxicities will be evaluated using the CTCAE grading scheme.

The overall incidence and intensity of adverse events, as well as relatedness of adverse events to treatment with BI 6727 monotherapy and in combination with cytarabine, respectively, will be reported for all treatment schedules.

Serious adverse events will be tabulated. In addition, events leading to dose reduction or treatment discontinuation will be examined, but may not be reported as individual tables, depending upon the extent of overlap with the occurrence of DLT.

Descriptive statistics will be used to describe changes in laboratory tests over time. In addition, all abnormalities of potential clinical relevance will be reported.

Events that started within the period starting with first administration of the trial drug and ending six weeks after the first treatment administration in the last treatment cycle will be considered as having occurred during treatment. In general, later events will be attributed to the post-study period and will be presented separately. However, post-study events will be examined to determine whether they need to be combined with on-treatment events in an additional table.

ECG measurements

Prolongation of QT/QTc times will be analysed descriptively and exploratory based on the ECG measurements described in [Section 5.2.7](#). Further details of the analysis of ECG data will be specified in the statistical analysis plan.

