5.2.7 Laboratory parameters

In this trial the original laboratory values will be converted into standard units and the CTCAE grades will be assigned to all parameters which have a CTCAE definition. For this study, the laboratory parameters and their functional groups, together with the direction of concern, which were to be recorded and which have a CTCAE criteria definition are:-

Haematology: Haemoglobin (HGB) (-), white blood cells (WBC) (-) and Platelets (-)

Differentials: Neutrophils (-) and Lymphocytes (-)

Electrolytes: Sodium (+ and -) and Potassium (+ and -)

Enzymes: AST (+), ALT (+), Alkaline Phosphatase (ALKP) (+), Troponin (TPONT) (+)

Substrates: Total bilirubin (+), Glucose (+ and -) and Creatinine (+)

Coagulation: International Normalised Ratio of prothrombin time (INR) (+) and Partial thromboplastin time (APTT) (+)

The signs + (-) means the above (below) the reference ranges.

It is important to note that these above described values are the only parameters that can be graded according to CTCAE criteria. The other parameters reported cannot be graded according to CTCAE criteria.

The change of the laboratory value will be calculated for all laboratory parameters from the baseline to the end of the treatment for the whole treatment duration. No post-study laboratory values will be considered.

Worst lab value and its CTCAE grade (highest CTCAE grade) over all courses will be calculated for each laboratory parameter specified above.

The last lab value on treatment is the lab value of the last visit of the last course of each patient.

The change of the CTCAE grade of the lab value will be calculated

- from baseline to the last lab value on treatment
- from baseline to the worst value on treatment

Note: For calculating the change in CTCAE grade from baseline/ pre-dose level, patients with a CTCAE grade of -9 at baseline will be reviewed on a case-by-case basis. If there is no evidence that the corresponding laboratory value is of clinical significance, these values will be changed to -7 and treated as a CTCAE grade of 0 for analyses. All other values with CTCAE grade -9 will be regarded as CTCAE grade -8. Values with a CTCAE grade of -8

will either be removed from analyses concerning determination of baseline and worst CTCAE grade or if needed the category “not covered by CTC criteria” will be included. Values with CTCAE grades of -7 and -8 will be displayed in two separate listings.

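### The protocol says duration of neutropenia will be evaluated; the SAP text available defines no such variable, plans no numerical summary of it by arm, and does not declare the omission

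*SAP*

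**What the plan says.** **Protocol.** Section 7.3.3 includes this among the safety analyses: "laboratory parameters, vital signs and duration of neutropenia will be evaluated". Section 1.4 explains why length matters. It notes that cytarabine and BI 6727 have overlapping toxicities and then says that "grade and duration of cytopenias and gastrointestinal toxicity will be important safety criteria to limit the risk". The same section describes the population: "AML patients often present with disease-related cytopenias, which without effective therapy will aggravate as the disease progresses". The exclusion criteria (3.3.2) set no minimum neutrophil or platelet count. The re-treatment criterion in 4.1.4 makes an exception, "unless CTCAE grade 4 neutropenia or thrombopenia was preexistent", and the haematological DLT in 5.2.3 makes a similar one.

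**SAP.** Section 5.2.7 states: "Worst lab value and its CTCAE grade (highest CTCAE grade) over all courses will be calculated for each laboratory parameter specified above". It also derives the change in grade to the last value and "from baseline to the worst value on treatment". Section 7.7.2 adds: "The baseline, last value on treatment and corresponding change from baseline will be presented using N, median and interquartile range". It further plans a summary of clinically relevant abnormalities and graphs over time by regimen, with neutrophils and platelets among the parameters plotted. Section 4, which lists departures from the protocol's planned analysis, does not mention duration of neutropenia.

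**The concern.** The protocol names a safety measure and gives a reason for it. The SAP text available never turns that measure into a variable: there is no onset rule, no recovery rule and no summary. If the SAP is followed as written, the randomised comparison in phase II will have no numerical result on how long neutropenia lasts in either arm.

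What remains is a weak substitute for this particular question. Worst grade and grade shift record depth, not length. In a patient who already has grade 4 neutropenia at entry, the shift to worst is zero whatever the treatment does. The last on-treatment value mixes marrow recovery, progression and early stopping. At stake is the safety side of the benefit-risk comparison. If one arm had longer neutropenia at a similar worst grade, the planned tables would give no figure for it.

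**Working it through.** The documents state no figure for duration, so there is none to reproduce. The check compares the texts and then does some short arithmetic.

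**1. Does another SAP output supply a duration?**

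| SAP output | What it gives | Duration by arm? |
|---|---|---|
| Baseline, last value, change (7.7.2) | Level at two time points | No |
| Worst value, worst grade, grade shift (5.2.7) | Depth | No |
| Clinically relevant abnormalities (7.7.2) | Patients summarised; definition in 9.1, not available | Not visible |
| Neutrophil and platelet time courses (7.7.2) | Graphs, which may be cut short if data are sparse | Display only |
| AE tables and listings (5.2.6, 7.7.1) | Episodes condensed to one worst-case record per term; episodes listed | Listing only |
| DLT (Protocol 5.2.3, SAP 7.7.1) | Yes/no | No |
| PK correlation with neutropenia (7.7.5) | Optional | No |

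AE dates would not fill the gap. Under Protocol 5.2.1 a laboratory change becomes an AE only if it is not tied to an event already reported and it leads to action with the drug or to treatment. The haematological DLT counts grade 4 cytopenia that persists to three weeks after the cycle, but only in patients with CRi or PR and without pre-existing grade 4. The dose-toxicity and time-to-DLT analyses in SAP 7.7.1 are set out for phase I.

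**2. What worst grade misses.** A 28-day cycle plus the three-week re-evaluation in Protocol 4.1.4 is 28 + 21 = 49 days. Grade 4 neutropenia for 5 days and for 49 days gives the same worst grade and the same shift. The DLT rule separates these two cases in CRi or PR patients without pre-existing grade 4, and in no one else.

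**3. Size of the ceiling effect (illustration; all rates assumed).** Let f be the share entering at grade 4. Among the others, let worst grade 4 occur in 60% of control and 85% of combination patients. The rate in an arm is then f + (1 − f)p. With n = 43 per arm (Protocol 7.6.2) and two-sided 5%,

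power = Φ{[d − 1.96√(2p̄(1−p̄)/n)] / √[(p₁(1−p₁)+p₂(1−p₂))/n]}.

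For f = 40% the rates are 0.4 + 0.6×0.60 = 0.76 and 0.4 + 0.6×0.85 = 0.91, so d = 0.15 and p̄ = 0.835. The two standard errors are 0.0801 and 0.0784. Power is Φ[(0.15 − 1.96×0.0801)/0.0784] = Φ(−0.088) = 0.46.

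| f | Worst grade 4, control vs combination | Power |
|---|---|---|
| 0% | 60% vs 85% | 75% |
| 20% | 68% vs 88% | 61% |
| 40% | 76% vs 91% | 46% |
| 60% | 84% vs 94% | 31% |
| 80% | 92% vs 97% | 17% |
| 100% | 100% vs 100% | 0% |

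For orientation, a 7-day difference in mean duration with an assumed SD of 10, 12 or 14 days would have power of 90%, 77% or 64% (for SD 12: SE = 12√(2/43) = 2.59 and Φ(7/2.59 − 1.96) = 0.77). The two sets of assumptions are separate, so this does not rank the measures.

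**4. The laboratory cut-off differs by arm.** SAP 5.2.7 excludes post-study values, and SAP Table 6.1.1: 1 starts post-study 21 days after the last dose. After a complete final course that is day 15 + 21 = day 36 in schedule A and day 10 + 21 = day 31 in schedule C. A duration cut at this limit would be followed 5 days longer in schedule A.

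**5. Precision from planned visits.** Counts are due on days 1, 5, 10, 15, 19, 23 and 28, so gaps are 4 or 5 days. With day 23 ± 2 and day 28 + 3, the last gap can run from day 21 to day 31, which is 10 days.

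**The case against.** The strongest reply is that the SAP does look at counts over time. It plots neutrophils and platelets by regimen, summarises relevant abnormalities, lists AE episodes and reports DLTs. All analyses are declared descriptive and exploratory (Protocol 7.2, SAP 3.3). SAP sections 9.1 and 9.2 and the in-house laboratory standard are cited but were not available, and a duration rule could sit there.

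Much of this stands. A reader might infer that the SAP analyses nothing beyond worst, last and change; the graphs and the abnormality summary show otherwise. A reader might also infer that the planned measures cannot separate the arms, or that worst grade sits at its ceiling in both. The documents do not support that. They say cytopenia at entry is frequent but give neither its grade nor a percentage. Patients entering below grade 4 remain informative, counts can still fall within grade 4, and in the illustration power reaches zero only if everyone enters at grade 4. Nor do the documents say that the combination prolongs neutropenia; Protocol 1.4 speaks of overlapping toxicity and transient cytopenias.

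None of this supplies the missing item. A graph or a listing is not a summary of duration by arm, and an exploratory analysis that the protocol names still needs a definition or a declared omission.

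**Conclusion.** The point holds in a limited form. The protocol commits to evaluating duration of neutropenia. The SAP text available contains no definition and no numerical summary by arm, and SAP section 4 does not record the change. The conclusion is conditional on SAP section 9 and the laboratory standard containing no such rule.

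Worst grade and grade shift are silent on length and cannot worsen in patients who enter at grade 4. How much this costs depends on a share the documents do not give; the 75%, 46% and 17% figures (at 0%, 40% and 80% entering at grade 4) rest on assumed rates and show direction only. The phase II response analysis is not affected. This is a cheap improvement that restores a measure the protocol already promised.

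**What to change.** In SAP 5.2.7 and 7.7.2, derive the time with neutrophils below 500/µL, using the limit already in Protocol 4.1.4. Do this for course 1, and per later course as support.

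- Summarise by arm in phase II, separately for patients with and without pre-existing grade 4 neutropenia. In the former, time to recovery also reflects remission and should be read that way.
- Use the same observation window in both arms, counted from the start of the course and including counts taken during a cycle delay. Do not cut at last dose + 21 days.
- Treat death, PD or new anti-leukaemia therapy before recovery as competing events, and present the cumulative incidence of recovery. Plain censoring would treat them as uninformative.
- Report G-CSF use alongside, since Protocol 4.2.1 allows it.
- Optional: the same for platelets below 25,000/µL, flagged for transfusion, and days of cycle delay for unrecovered counts.

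The cost is SAP wording and one derived data set, from counts already scheduled. The drawback is coarse timing: durations are known only to the visit spacing, usually 4–5 days and up to about 10 with the visit windows. Protocol 4.1.4 gives no fixed schedule for rechecks during a delay.

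If the sponsor prefers not to add this, SAP section 4 should state that the protocol measure was dropped, and why.

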7.7.3 Vital signs

Descriptive statistics of absolute values (and change from baseline) of vital signs (including body weight at baseline) will be provided by treatment group, for actual time and visit over all courses. Vital signs during infusion will be analysed descriptively.

7.7.4 ECG / QTc

Newly emergent abnormalities will be recorded and analyzed as adverse events.

7.7.4.1 Derivation of ECG endpoints

Three replicate digital ECG recordings will be collected at each time-point. Each of the three recorded single ECGs will then be evaluated for cardiac intervals, which comprise the RR, PR, QT interval and QRS duration. Measurements of these intervals will be made on four (possibly consecutive) waveforms from the lead chosen (usually lead II). The measurements of the waveforms will be stored in the database, i.e. twelve values per time-point. The four waveforms will be averaged prior to the calculation of the heart rate and heart rate corrected QT intervals. Further aggregation of the three replicate QT/QTc intervals and heart rates at each scheduled time-point will be performed using arithmetic means. These values will be used for the derivation of the ECG endpoints as they are specified in [Section 5.3.5](#).

The heart rate will be derived from the RR interval as

$$\text{HR [bpm]} = 60000/\text{RR [ms]}$$

For each QT interval, the RR interval preceding the QT interval will be used for frequency correction.

Heart rate corrected QT intervals (generally denoted as QTc) will be calculated using Fridericia's (QTcF) and Bazett's formulas (QTcB):

$$\text{QTcF [ms]} = \left(\frac{1000}{\text{RR}} \right)^{\frac{1}{3}} * \text{QT [ms]},$$

and

$$\text{QTcB [ms]} = \left(\frac{1000}{\text{RR}} \right)^{\frac{1}{2}} * \text{QT [ms]}$$

7.7.4.2 ECG Analysis

Absolute values and change from baseline in QTcF, QTcB, QT, PR intervals, HR, and QRS duration will be summarised descriptively by course for the MTD groups (including patients treated at the MTD in Phase II) using the Treated Set.

Frequencies of the increases in QTcF/QTcB/QT intervals above thresholds such as 450 ms, 470 ms and 500 ms between baseline and on-treatment will be displayed in two-way shift-tables by initial dose for the Treated set.

Frequencies of patients with increases from baseline in QTcF, QTcB and QT intervals above the defined thresholds and notable findings will be displayed, as well.

Frequency tables by overall clinical interpretation and findings possibly impacting interval measurement, and a new onset (not present at baseline) of an abnormal finding will be generated.

7.7.5 Pharmacokinetics

The analysis of standard PK parameters is performed according to [2].

The distribution of BI 6727 plasma concentrations will be graphically inspected and summarised by time point in the CTR.

If felt necessary based on the clinical outcome, BI 6727 pharmacokinetic parameters (Cmax, exposure, eg AUC) will be correlated with the observed neutropenia, leukopenia and leukemic myeloblasts.

7.7.6 Others

If considered necessary, the number of patients who died, and the number of patients who are lost to follow-up will be listed by treatment regimen at follow-up-visits.

Blood products used will be listed by patient.

